4.11.2 Prohibited Treatments

Treatment with any other experimental drug or a concomitant chemotherapy, anticancer hormonal therapy, radiotherapy, or immunotherapy is prohibited during study participation. This includes additional doses of rituximab or SAIT101 after the initial 4-weekly doses.

If a patient requires tumor targeting treatment for FL other than the protocol-defined treatment with rituximab or SAIT101 monotherapy due to disease progression based on tumor assessments done at investigational site, he or she will be considered as a treatment failure and should be discontinued from the study treatment. (See Section 3.3.1.2) Patients with progressive disease should be treated with an adequate therapy according to judgment of the treating physician. In such case, patient will be followed-up until Week 52 (EOS) for safety and immunogenicity.

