8.8 Efficacy Analyses

The statistical analysis of the primary endpoint for this study will be performed after the last patient has completed the Week 28 response assessment. All efficacy data will be analyzed at this time, plus all PK, PD, immunogenicity, and safety data available at the time of data

cut-off, and these data will be reported in the CSR (Week 28 CSR). After the last patient has completed Week 52 of the study, a CSR addendum (Week 52 CSR) will be prepared to report the additional safety data.

Efficacy will be assessed centrally as CR, PR, SD, and PD, as defined in IWG criteria 2007, and TTE. The main efficacy endpoint will be the difference in ORR (CR+PR) at Week 28, approximately 24 weeks after the completion of study treatment. The efficacy analyses will be applied for both the PP set and FAS. FAS will be considered as primary efficacy analysis population and analysis in PP set will be conducted as a sensitivity analysis.

In FAS, patients without a response assessment at Week 28 will be handled using a conservative approach by imputation using drop-out reason (IUDR), where Non-responder imputation (NRI) method in case of treatment related reasons and otherwise multiple imputation (MI) procedure assuming missing at random (MAR) will be applied. For the PP set, all available data will be used for analysis.

Potential withdrawal reasons are considered as follows based on previous studies; The major reason of missing response assessment at Week 28 is assumed to be either the start of new treatment of FL due to lack of efficacy or toxicity based on Ardeshtna et al. In such reasons related to treatment (i.e. treatment failure requiring tumor targeting treatment for FL other than the protocol-defined treatment, death due to progressive disease), patients without a response assessment at Week 28 will be handled as non-responders. Missing responses unrelated to treatment (i.e. withdrawal by subject, pregnancy) as seen in the Colombat et al. would be considered ignorable missing at random (MAR) and multiple imputation procedure using logistic regression method will be used to impute the missing response assessment at Week 28 (responder versus non-responder). No imputation will be applied when the reasons are unknown whether they are related to treatment or not (i.e. lost to follow-up).

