2.7. Phone Visit

As a measure to minimize lost to follow-up, a phone visit can be tried.

- ECOG performance status assessment
- Concomitant medications.
- Adverse events.

APPENDIX 11: DEFINITION OF PROGRESSION THAT WARRANTS INITIATION OF TREATMENT CHEMOTHERAPY/RADIOTHERAPY.

Modified based on the publication:

Ardeshta KM1, Qian W, Smith P, Braganca N, Lowry L, Patrick P, Warden J, Stevens L, Pocock CF, Miall F, Cunningham D, Davies J, Jack A, Stephens R, Walewski J, Ferhanoglu B, Bradstock K, Linch DC. Rituximab versus a watch-and-wait approach in patients with advanced-stage, asymptomatic, non-bulky follicular lymphoma: an open-label randomised phase 3 trial. *Lancet Oncol.* 2014; 15: 424-35.

It is recognized that it is difficult to clearly define when disease progression is sufficient to warrant the initiation of chemotherapy or radiotherapy. The following is suggested guidance:

1. Development of symptomatic enlarged lymph nodes or spleen.
2. The development of B symptoms or severe pruritus.
3. Lymphomatous mass >7cm provided it has increased in size by at least 25%.
4. More than 3 sites with diameter >5cm.
5. The development of significant serous effusions, clinically or on CT (small, clinically non-evident effusions on CT scan are not an indication to start chemotherapy).
6. Hemoglobin <100g/L (10g/dL), absolute neutrophil count <1.5x10⁹/L (1,500/mm³), platelet <100x 10⁹/L (100,000/mm³) not attributable to other causes. If asymptomatic this should persist for >1 month.
7. Critical or near critical organ involvement or organ compression, e.g. ureteric obstruction, epidural compression.
8. A rising LDH is not in itself an indication to initiate therapy but may trigger further investigations.

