### 2.3. SAMPLE SIZE CALCULATION

Response rate of MabThera® 4 weekly dosing in low tumor burden follicular lymphoma was assessed in Ardeschna et al. 2014, Kahl et al. 2014 and Colombat et al. based on systematic literature search. The Ardeschna study was the only randomized trial which compared the treatment of MabThera® alone with the ‘watch & wait’ (W&W). The month 7 response rate on MabThera® monotherapy was estimated to be 77% with 95% confidence interval (CI) (66%-85%), considering the lower bound of 95% CI of response rate to be 66%, the highest non-response rate of MabThera® is estimated as 34%. Assuming the rate of non-responders with SAIT101 will not exceed 1.5 times over the expected highest non-response rate with MabThera® at 34%, the equivalence can be declared if the non-response rate in the SAIT101 arm is less than 51%. In other words, with the lower bound of 95% CI of responder rate of MabThera® at 66%, equivalence can be declared if the response rate in the SAIT101 arm is more than 49%. As above, the estimated margin should be set less than ±17.0%.

In the reference study, the month 7 response rate in MabThera® monotherapy was estimated to be 77% with 95% CI (66%-85%) and response rate of W&W group was estimated to be 6%, giving an estimated difference in overall response rate (ORR) of 71% with 95% CI (59%-79%). The equivalence margin of ±16.0% ( $0.59 \times [1-0.73] = 0.1593$ ) was calculated to preserve at least 73% of the treatment benefit of MabThera® based on the lower bound of 95% CI of the difference in ORR.

Document:

Author:

Version Number:

Version Date:

Final v1.0

10Sep2019

Template No: CS\_TP\_BS016 Revision 4

Effective Date: 01Apr2016

Reference: CS\_WI\_BS005

To achieve 83% power with a 16.0% margin and a 77% expected ORR with 2 one-sided tests at the significance level of 0.025. nQuery Advisor 4.0 calculated the following with the given assumption: With 154 patients in each group, the observed 2-sided 95.0% CI will be expected to lie between -0.160 and 0.160 with 83% power when the Standard proportion,  $P_s$ , is 0.770 and the Test expected proportion,  $P_t$ , is 0.770; results are based on 1,000 simulations using the Newcombe-Wilson score method to construct the CI.

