Thus, 154 patients in each group are able to satisfy the primary analysis of ORR, given an 83% probability of declaring equivalence in the full analysis set (FAS). Patients who discontinue the study drug early for any reason will be required to have efficacy assessments at Week 28. Allowing for a 4% drop-out rate and patients with major protocol deviations as seen in the Ardeschna et al, 147 patients in each group will give 80% probability of demonstrating equivalence in the PPS.

At least 154 patients per arm (308 patients overall) should be randomized into the study. With 154 patients, the estimated ORR with 95% CI of SAIT101 is 77% (70%-84%). ORR with 95% CI of MabThera® based on a random effect meta-analysis that include Ardeschna et al. 2014, Kahl et al. 2014 and Colombat et al. 2001 was estimated as 72% (68%-76%). The maximum difference in the upper and lower 95% CI of ORRs is  $\pm 15.0\%$ , which is smaller than the margin  $\pm 16.0\%$ , and this estimated ORR with 95% CI for SAIT101 is considered to exclude a clinically relevant. difference versus MabThera.

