## 5.3. RETESTS AND UNSCHEDULED VISITS DATA

Generally, data recorded at the nominal visit will be presented for by-visit summaries.

Unscheduled measurements will not be included in by-visit summaries, but will contribute to the best/worst case value where required (e.g. shift table).

In the case of a retest (same visit number assigned), the latest available measurement of non-PK/PD assessments for that visit will be used for by-visit summaries.

If the patient discontinued treatment during the study after Day 1 and the next visit data is missing, then early termination data, i.e. early treatment discontinuation visit data, will be mapped to the next available visit number for by-visit summaries. Otherwise, early termination data will not be mapped.

Listings will include scheduled, phone visit, unscheduled, retest and early study discontinuation data in chronological order. Listings will include all scheduled, unscheduled, retest, early discontinuation and phone visit data.

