## 16. Efficacy Outcomes

### 16.1. PRIMARY EFFICACY

#### 16.1.1. PRIMARY EFFICACY VARIABLE & DERIVATION

The primary efficacy variable is the difference in Overall Response Rate (ORR) at Week 28, approximately 24 weeks after the completion of study treatment.

ORR is defined as the proportion of patients with complete response (CR) or partial response (PR) as assessed by central imaging review per IWG criteria 2007 until Week 28 after the start of treatment. ORR will be evaluated for each patient separately from the date of first administration of trial medication (i.e. Day 1) until either progression, death or up to Week 28 (i.e. study day 204 = 190+14), whichever happens earlier. Per protocol, CT scan (neck, chest, abdomen, pelvis, and any other areas known or suspected to be involved) with contrast to be conducted at screening, Week 12 and Week 28 (assessment permitted up to 4 weeks prior to, or 2 weeks after the Weeks 12 and 28 visit).

Patients who start subsequent anticancer therapy will typically have progressed or stopped treatment due to unacceptable toxicity. A CT scan should be conducted at their early treatment discontinuation visit. In the case where a patient starts subsequent anti-cancer therapy but the ORR evaluation period of that patient is still ongoing, the patient's ORR will be evaluated only until the start of subsequent anti-cancer therapy.

Unscheduled assessments recorded during the evaluation period for ORR will be taken into account for determination of ORR. Tumor assessments started on study day 204 but not completed on study day 204 will be fully included in the evaluation of best ORR.

The primary endpoint will be analyzed as described in section 16.1.3 and sensitivity analyses for the primary efficacy analysis will be performed as described in section 16.1.4.

---

Document:

Author:

Version Number:

Version Date:

Final v1.0

10Sep2019

Template No: CS\_TP\_BS016 Revision 4

Effective Date: 01Apr2016

Reference: CS\_WI\_BS005

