### **16.1.2. MISSING DATA METHODS FOR PRIMARY EFFICACY VARIABLE**

The imputation of ORR will follow Imputation Using Drop-out Reason (IUDR). The imputation rules for the IUDR imputation of ORR will be as follows:

Following the start of a new treatment for FL, either due to lack of efficacy or treatment-related toxicity reasons (i.e. treatment failure requiring tumor targeting treatment for FL other than the protocol-defined treatment or death due to progressive disease), patients without a response assessment at Week 28 will be considered as non-responders.

Overall tumor assessments by central imaging review will be assessed as CR, PR, stable disease (SD), progressive disease (PD), Unknown, and No Evidence of Disease (NED). Missing or non-evaluable response assessments (i.e. UNK and NED) will not be imputed and will be considered as non-responders.

Missing responses unrelated to treatment (i.e. withdrawal by patient, pregnancy) will be considered ignorable missing at random (MAR) and multiple imputation procedure using logistic regression method will be used to impute the missing response assessment at Week 28 (responder versus non-responder).

No imputation will be applied when the reasons are unknown for treatment related or not (i.e. lost to follow-up).

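### A response seen before new lymphoma treatment can be carried into the primary Week 28 response rate, because non-response is imposed only when the Week 28 assessment is missing

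*SAP*

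**What the plan says.** The protocol's primary endpoint is centrally assessed ORR at Week 28 (2.3.1, 8.8). SAP 16.1.1 keeps that name but defines response as a central CR or PR within a period that runs from Day 1 to the earliest of progression, death or study day 204. Unscheduled scans count, and the section speaks of *best ORR*. If new therapy starts within the period, "the patient's ORR will be evaluated only until the start of subsequent anti-cancer therapy". That sentence discards later scans but gives the patient no status.

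Other sections deal with the same patient:

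- Protocol 4.11.2, on a patient who needs other tumour-directed FL treatment because of progression on site assessments: "he or she will be considered as a treatment failure".
- Protocol 8.8, for treatment-related reasons: "patients without a response assessment at Week 28 will be handled as non-responders".
- SAP 16.1.2, after new FL treatment for lack of efficacy or toxicity: "patients without a response assessment at Week 28 will be considered as non-responders". Central reads of unknown or no evidence of disease are also non-response.
- Protocol Table 1, footnote c: patients who stop study drug early have efficacy assessments at Week 28 or before new anti-lymphoma treatment.
- SAP 5.3, where the next visit's data are missing: "early treatment discontinuation visit data, will be mapped to the next available visit number for by-visit summaries".
- SAP 16.2.1: the start of new FL treatment is an event for TTE.

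**The concern.** Protocol 8.8 and SAP 16.1.2 show the intent that a patient who needed new FL treatment should not count as a success at Week 28. The rule is written as a missing-data rule, however, so it acts only when the assessment is absent. Once a Week 28 assessment exists, 16.1.1 governs, and it can keep a response from before the new treatment. The score then depends on whether the patient attended a scan after failing, which says nothing about the study drug.

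This matters more in an equivalence trial than in a superiority trial. Scoring failures as responders can shrink a real difference between the arms, and a smaller difference favours the claim the trial is meant to test.

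**Working it through.** **Scoring.** Take patients who start new FL treatment around or before Week 28.

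| Patient | SAP 16.1.1 | SAP 16.1.2 | Score |
|---|---|---|---|
| A. Central SD or PD only before new treatment | No CR/PR | Not needed | Non-responder |
| B. Central PR at Week 12, new treatment, no Week 28 scan | PR lies in the period | Applies | Non-responder |
| C. Central PR at Week 12, new treatment, Week 28 scan done | Week 28 scan discarded, Week 12 PR stands | As worded, does not apply: an assessment exists | Responder |
| D. As C, with the discarded scan treated as absent | As C | Would apply | Non-responder, but the SAP does not state this step |
| E. Scan inside the Week 28 window reads PR, then new treatment | PR at the Week 28 assessment | Not needed | Responder, properly |

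B and C have the same clinical course up to the scan but opposite scores. C is the gap.

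**Planned analyses (SAP Table 1).** Analyses 1-1, 3 and 4 change only how a missing Week 28 value is handled. Analyses 2-1 and 5-1 change only the method. None rescores C. The PPS analyses (1-2, 2-2, 5-2) may drop C as prohibited treatment, but that is subject to a judgement of clinical relevance, and it removes the patient rather than scoring a failure.

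**The plan's own power.** Inputs from SAP 2.3: 154 per arm, 77% in both arms, margin 16 points, "with 2 one-sided tests at the significance level of 0.025".

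- Normal approximation: SE = sqrt(2 × 0.77 × 0.23 / 154) = 0.0480. Power = 2Φ(0.16/0.0480 − 1.96) − 1 = 83.1%.
- Exact enumeration of the two binomials with the unstratified Newcombe-Wilson 95% CI: 84.0%.
- Stated: 83%. The figure reproduces.

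**Shift per patient.** 1/154 = 0.65 points of one arm's ORR. With k_T and k_R patients of type C in the SAIT101 and MabThera arms, the observed difference minus the correctly scored one is (k_T − k_R)/154. Equal counts give no shift. An assumed excess of 5 in the SAIT101 arm gives 5/154 = 3.2 points, a fifth of the margin; all five would need a central CR or PR beforehand.

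**Near the limit.** Take 119/154 (77.3%) responders on MabThera, unstratified.

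- 9 fewer on SAIT101: −5.8 points, CI −15.5 to 3.9, equivalent.
- 10 fewer: −6.5 points, CI −16.1 to 3.3, not equivalent.

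**False equivalence.** Assume a share r of true non-responders in each arm is scored as responders, with a true difference of −16 points (61% v 77%). The observed rates are 0.61 + 0.39r and 0.77 + 0.23r, so the observed difference is −16(1 − r) points. The patients misscored are 154 × 0.39r and 154 × 0.23r.

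| r (assumed) | Misscored, SAIT101 / MabThera | Observed difference | P(equivalence declared) |
|---|---|---|---|
| 0 | 0 / 0 | −16.0 | 2.7% |
| 5% | 3.0 / 1.8 | −15.2 | 3.8% |
| 10% | 6.0 / 3.5 | −14.4 | 5.3% |
| 20% | 12.0 / 7.1 | −12.8 | 10.2% |

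**The case against.** **The affected group is narrow.** SAP 16.1.1 itself says that patients who start new therapy will typically have progressed or stopped for toxicity. Those read centrally as SD, PD, unknown or no evidence of disease are already non-responders. Protocol 4.11.2 describes follow-up after new treatment as being for safety and immunogenicity, so some of these patients will have no Week 28 scan and fall under 16.1.2. All of this stands. It limits the number affected but does not settle case C.

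**Response up to new therapy is a coherent definition, and TTE need not score patients the same way.** Both are true in general. But the endpoint is named for Week 28, and 16.1.2 has already chosen non-response for these patients. The conflict is within the SAP. TTE and the listing of new treatments would reveal an imbalance, though only indirectly.

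**Stronger readings that the documents do not support.**

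- *A response produced by the new treatment counts.* Protocol 8.8 alone leaves this open, but SAP 16.1.1 discards scans after new therapy starts. Under the SAP the risk is an earlier response carried forward.
- *SAP 5.3 turns the discontinuation scan into a Week 28 response.* The mapping is stated for by-visit summaries, and 16.1.1 does not invoke it. Its use for ORR is at most unaddressed.
- *The symptom triggers in Appendix 11 show protocol-defined failures being scored as responders.* An entry such as "The development of B symptoms or severe pruritus" does not by itself meet 4.11.2, which requires progression on site tumour assessments. Case C does not need this argument.
- *The rule must bias towards equivalence.* The direction depends on the balance between arms. If more MabThera patients are misscored, SAIT101 looks worse.

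**Conclusion.** The point holds in this form. As written, the SAP can score as a Week 28 responder a patient whose response came before new FL treatment, provided a Week 28 assessment was done. It would score the same patient a non-responder had that assessment been missed. Where the new treatment was for site-assessed progression, this also conflicts with protocol 4.11.2. No planned analysis rescores these patients.

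The firm size is 0.65 points of one arm's ORR per patient. How many patients are affected is not in the documents, so the error rates of 3.8% to 10.2% are illustrations. They rest on an assumed share r of 5% to 20%, equal in both arms, and on an unstratified interval, whereas the primary analysis is weighted by FLIPI-2 group. With a result well inside the margin, a few such patients would not change the conclusion. Near the limit, one could.

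If the sponsor already means a scan after new treatment to count as absent (case D), the gap closes in intent, but the SAP must say so.

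**What to change.** - In SAP 16.1.1 and 16.1.2, and in protocol 8.8, state that a patient who starts new treatment for FL before the Week 28 response scan is a non-responder for ORR at Week 28, whatever other scans exist.
- In SAP 16.1.1, delete the *until Week 28* and *best ORR* wording, or state that response is the one read at the Week 28 assessment.
- State that the by-visit mapping in SAP 5.3 does not create a Week 28 response for these patients.
- Replace *anti-cancer therapy* with *new treatment for FL*, as in the TTE definition, so that treatment of another malignancy does not trigger the rule.

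The cost is a few sentences and one derivation flag; new anti-lymphoma treatment is already to be listed (SAP 17.7). The margin and the planned 154 per arm do not change. Observed ORR may be slightly lower in both arms, which costs some power. As an illustration, if the rate fell from 77% to an assumed 75% in both arms (about 3 patients each, 3/154 = 1.9 points), SE = sqrt(2 × 0.75 × 0.25 / 154) = 0.0493 and power = 2Φ(0.16/0.0493 − 1.96) − 1 = 80.0%, against 83.1% on the same approximation.

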### **16.1.2. MISSING DATA METHODS FOR PRIMARY EFFICACY VARIABLE**

The imputation of ORR will follow Imputation Using Drop-out Reason (IUDR). The imputation rules for the IUDR imputation of ORR will be as follows:

Following the start of a new treatment for FL, either due to lack of efficacy or treatment-related toxicity reasons (i.e. treatment failure requiring tumor targeting treatment for FL other than the protocol-defined treatment or death due to progressive disease), patients without a response assessment at Week 28 will be considered as non-responders.

Overall tumor assessments by central imaging review will be assessed as CR, PR, stable disease (SD), progressive disease (PD), Unknown, and No Evidence of Disease (NED). Missing or non-evaluable response assessments (i.e. UNK and NED) will not be imputed and will be considered as non-responders.

Missing responses unrelated to treatment (i.e. withdrawal by patient, pregnancy) will be considered ignorable missing at random (MAR) and multiple imputation procedure using logistic regression method will be used to impute the missing response assessment at Week 28 (responder versus non-responder).

No imputation will be applied when the reasons are unknown for treatment related or not (i.e. lost to follow-up).

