Patients with low tumor burden follicular lymphoma (LTBFL) have a 10-year survival rate of 75%,¹ and clinical outcome has improved in recent years with the introduction of rituximab. However, some patients are asymptomatic for many years, while others quickly present with a life-threatening disease. Because of this heterogeneity, it is important to stratify patients for treatment decisions based on tumor burden criteria, such as those of the Groupe D'Etude des Lymphomes Folliculaires (GELF), and the Follicular Lymphoma International Prognostic Index-2 (FLIPI-2) (see Appendix 3). Based on these criteria, patients with low tumor burden (LTB) may have local or systemic therapy delayed until disease progression – a “watchful wait” strategy. In patients with high tumor burden, combination treatment with rituximab and cyclophosphamide, doxorubicin, vincristine, and prednisone/prednisolone (R-CHOP) or other regimens has resulted in superior treatment outcomes compared with multi-agent chemotherapy alone. Combined immunochemotherapy with rituximab has thus become the new standard of care for high tumor burden patients. The optimal timing of treatment for advanced, asymptomatic, FL is still to be determined, however. Before rituximab became available, patients with asymptomatic, advanced-stage FL showed no benefit with immediate chemotherapy compared with watchful-waiting, and watchful-waiting became the accepted standard of care. Recent data, however, have shown a benefit of first line rituximab monotherapy in delaying chemotherapy treatment in patients with

LTBFL.^{2,3} Furthermore, this benefit could be achieved with just 4 injections of rituximab (once a week for 4 weeks), and no maintenance treatment. However, rituximab is not yet approved for monotherapy use in LTBFL.

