**Table 1 – Primary analysis and sensitivity analyses for the primary efficacy endpoint**

Analyses for primary endpoint	Analysis Set	Analysis Method	Stratification factors included	Imputation method for missing value at Week 28
Primary analysis	FAS	95% Newcombe-Wilson CI using the CMH weighted method	FLIPI-2 score group	IUDR
Sensitivity analysis 1-1	FAS	Same as primary	Same as primary	No imputation
Sensitivity analysis 1-2	PPS	Same as primary	Same as primary	NA
Sensitivity analysis 2-1	FAS	95% Newcombe-Wilson CI	None	Same as primary
Sensitivity analysis 2-2	PPS	95% Newcombe-Wilson CI	None	NA
Sensitivity analysis 3	FAS	Same as primary	Same as primary	NRI
Sensitivity analysis 4	FAS	Same as primary	Same as primary	MI

Document:  
 Author:

Version Number:  
 Version Date:

Final v1.0  
 10Sep2019

Template No: CS\_TP\_BS016 Revision 4  
 Effective Date: 01Apr2016

Reference: CS\_WI\_BS005

Sensitivity analysis 5-1	FAS	Logistic regression model along with Delta method	Same as primary	Same as primary
Sensitivity analysis 5-2	PPS	Logistic regression model along with Delta method	Same as primary	NA

NRI= Non-responder imputation, MI= multiple imputation; IUDR= imputation using drop-out reason (NRI for missing due to treatment-related reason, MI using logistic regression assuming ignorable missing at random (MAR) for missing due to reasons unrelated to treatment, and no imputation when the reasons are unknown whether they are related to treatment or not).

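### SAP 16.1.2 applies the non-response rule more narrowly than the imputation rule it implements, so a toxicity exit with no Week 28 scan and no new FL treatment is unassigned and can be multiply imputed

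*SAP*

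**What the plan says.** The primary analysis imputes missing Week 28 responses by drop-out reason (IUDR). The rule is stated at two levels.

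**General rule.** Protocol 8.8 prescribes "Non-responder imputation (NRI) method in case of treatment related reasons and otherwise multiple imputation (MI) procedure". The footnote to SAP Table 1 reads "NRI for missing due to treatment-related reason, MI using logistic regression assuming ignorable missing at random (MAR) for missing due to reasons unrelated to treatment". Neither makes new FL treatment a condition of non-response.

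**Detailed rules in SAP 16.1.2.**
- Non-response applies "Following the start of a new treatment for FL, either due to lack of efficacy or treatment-related toxicity reasons". A parenthesis then limits this to treatment failure needing other tumor-directed FL therapy, or death from progression. The examples in Protocol 8.8 name the same two cases.
- A second route to non-response carries no condition on new FL treatment: "Missing or non-evaluable response assessments (i.e. UNK and NED) will not be imputed and will be considered as non-responders".
- MI by logistic regression is kept for a separate class, in these terms: "Missing responses unrelated to treatment (i.e. withdrawal by patient, pregnancy) will be considered ignorable missing at random (MAR").
- Where the cause of the exit is not known, the section says: "No imputation will be applied when the reasons are unknown for treatment related or not (i.e. lost to follow-up").

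**Routes out of the study.** Protocol 3.3.1.1 lists three reasons for leaving the study: withdrawal of consent (which the patient need not justify), loss to follow-up, and closure of the study or site by the sponsor. Toxicity is not listed. Protocol 3.3.1.2 covers stopping study drug, where a Week 28 efficacy assessment is still required. Protocol Appendix 8, by contrast, has a patient who cannot tolerate the reduced infusion rate discontinued from the study.

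**The concern.** The detailed rule does not cover everything the general rule covers. Consider a patient who has a drug-related reaction, leaves the study, has no Week 28 scan and starts no new FL treatment. The last condition is realistic here: Protocol 1.1.1 says "patients with low tumor burden (LTB) may have local or systemic therapy delayed until disease progression". The general rule makes this patient a non-responder. The detailed sentence does not reach the case, because no new FL treatment began and the patient did not die of progression.

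Since toxicity is not a listed reason for leaving the study, the exit may be recorded as withdrawal by patient, which SAP 16.1.2 names as unrelated to treatment and sends to MI. The response is then drawn from a model fitted to patients who were assessed. The SAP names no covariates for that model, so the draw would run near the observed response rate.

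The stake is the single primary comparison. Protocol 8.8 presents IUDR as conservative. If toxicity exits were more frequent on the test product, treating them as ignorable would shrink an observed deficit, and in an equivalence trial a smaller difference favors success.

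**Working it through.** **Inputs from the documents.** 154 patients per arm; expected ORR 77% in both arms; margin ±16 points; two-sided 95% Newcombe-Wilson interval (SAP 2.3 and 16.1.3). A combined 4% allowance for drop-out and major deviations (SAP 2.3).

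**Assumed.** The share of an arm that leaves for drug toxicity with neither a Week 28 scan nor new FL treatment. The documents give no figure.

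**Step 1: reproduce the plan's power.** Summing two binomials (n = 154, p = 0.77) over all outcomes whose unstratified Newcombe-Wilson interval lies inside ±0.16 gives 84.0%. The normal approximation 2Φ(0.16/SE − 1.96) − 1, with SE = √(2 × 0.77 × 0.23/154), gives 83.1%. The stated figure is 83%. At 147 per arm the enumeration gives 81.3%, against a stated 80%.

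**Step 2: effect per patient.** Moving one patient from non-response to MI at about 77% adds 0.77/154 = 0.5 points to that arm's ORR. For 1% to 4% of one arm, the shift is 0.77 × share, or 0.8 to 3.1 points.

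**Step 3: when that matters.** With 119/154 responders on reference, the test arm passes at 110/154 (interval −15.5 to +3.9 points) and fails at 109/154 (−16.1 to +3.3). A few patients decide the result only near this boundary.

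**Step 4: false equivalence at the margin.** Take true ORRs of 61% (test) and 77% (reference), counting toxicity losses as non-response. Imputing a lost share q at the assessed patients' rate raises an arm's expected ORR from p to p/(1 − q). The Newcombe-Wilson rule is then enumerated at the shifted rates with 154 per arm.

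| Losses, test v reference (assumed) | Shifted ORRs | Difference (points) | Equivalence declared |
|---|---|---|---|
| scored as non-response | 61.0% v 77.0% | −16.0 | 2.7% |
| 2% v 1% | 62.2% v 77.8% | −15.5 | 3.3% |
| 3% v 1% | 62.9% v 77.8% | −14.9 | 4.3% |
| 4% v 1% | 63.5% v 77.8% | −14.2 | 5.7% |
| 5% v 1% | 64.2% v 77.8% | −13.6 | 7.3% |
| 2% v 2% | 62.2% v 78.6% | −16.3 | 2.3% |

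Equal losses leave the error rate essentially unchanged.

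**Step 5: power if these patients are scored as non-responders instead.** With true equivalence at 77% and 1%, 2%, 3% or 4% of one arm affected, power goes from 84.0% to 82.9%, 80.8%, 77.6% or 73.6%. With both arms equally affected it is 82.9%, 81.8%, 80.7% or 79.6%.

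All of these calculations are unstratified; the planned analysis is stratified by FLIPI-2.

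**The case against.** A reader might infer that the plan multiply imputes every toxicity exit without new FL treatment. The documents do not say that. SAP 16.1.2 limits MI to reasons unrelated to treatment, a drug-related reaction is by definition related, and both statements of the general rule give non-response. MI follows only if the parenthetical examples are read as exhaustive and Protocol 8.8's residual MI clause then applies, or if the exit is recorded as withdrawal by patient. This objection stands: the case is unassigned, and MI is one possible outcome.

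It may also be said that the sentence scoring missing or non-evaluable assessments as non-response already catches these patients. It follows a list of central-review categories and is qualified by UNK and NED, so it reads most naturally as covering scans that were read. If it covered absent scans, the MI and no-imputation rules after it would have nothing to act on. It does not settle the case, and it needs rewording either way.

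The mitigations are real. Patients who stop drug must still be assessed at Week 28, and an assessment is strongly encouraged before formal withdrawal. SAP 16.1.1 evaluates response up to Week 28 and counts unscheduled scans, so a leaver with an earlier scan may not be missing. Sensitivity analysis 3 scores every missing value as non-response, although equivalence is declared on the primary analysis.

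The magnitude is also fairly challenged. The plan's 4% allowance covers all drop-outs and major deviations together, so 4% in one arm for this subtype alone is an upper-end case and 5% exceeds the allowance. The truth is placed at the margin, and is defined by counting toxicity losses as non-response, whereas the IWG criteria describe imaging response. Nor does non-response scoring always protect: more toxicity losses on reference would lower the reference ORR and could hide a test-arm deficit. Finally, nothing in the documents shows that toxicity exits will differ between arms.

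**Conclusion.** The detailed rule in SAP 16.1.2 conflicts with the definition of IUDR it is meant to implement. One identifiable kind of patient is left unassigned and can reach MI under the written rules through the recorded exit reason. This should be settled before unblinding.

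The effect is about 0.5 ORR points per patient and matters only when such losses differ between arms and the result lies near the boundary. The 3% to 7% false-equivalence range depends on assumed losses of 2% to 5% against 1%, a true difference exactly at the margin, and an unstratified calculation. It shows sensitivity to the rule. It does not forecast this trial, and the documents do not support a claim of demonstrated bias toward equivalence.

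**What to change.** Restate the rule in SAP 16.1.2. A patient without a Week 28 response assessment is a non-responder if the patient:

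- (a) started new treatment for FL;
- (b) died of progressive disease; or
- (c) discontinued study drug or left the study because of an adverse event assessed as related to study drug, whether or not new FL treatment was started, and even if the exit is recorded as withdrawal by patient.

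Assign (c) at the blinded data review, using the action-taken and causality fields (SAP 17.1) and the withdrawal reasons (SAP 8). Reserve MI for exits in which no related adverse event was the cause. Confine the sentence on UNK and NED to scans that were performed but could not be evaluated, so that it no longer overlaps the MI and no-imputation rules.

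The cost is a few sentences in the SAP and no new data. ORR and power may fall slightly, as in step 5 of the working. Toxicity exits with no recorded reason will still be missed, since a patient who withdraws consent need not give one; sensitivity analysis 3 remains the check on those.
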